11.2.3 Workstream 2b

We will summarise key characteristics of women who experience these events, including demographics, clinical characteristics, vital signs measurements, and type of event. We will describe when women in MBRRACE-UK meet the new outcome criteria, prior to the extreme outcomes that result in inclusion in

the MBRRACE-UK dataset. For each existing MOEWS/MEWS, we will calculate sensitivity at pre-defined thresholds and assess how early women alert prior to the events occurring, if at all. Where sufficient data exist, we will examine performance in key subgroups. Missing vital sign data will be handled similarly to WS2a.

11.2.4 Workstream 3b

11.2.4.1 Model development

We will explore both regression and machine learning (ML) approaches for model development. We anticipate at least 5800 ‘near-miss’ or ‘severe morbidity’ events, with higher rates using our new definitions.

For approaches using regression models (e.g., logistic or Cox regression if censoring is an issue) we will assess pre-defined pairwise interactions and include non-linear relationships for continuous predictors (e.g., using fractional polynomials or restricted cubic splines) (66). Pairwise interactions may be used to address apparent discrepancies in model performance for specific subgroups, identified in WS2. We will investigate whether accounting for trends of repeated measurements within individuals (e.g., blood pressure) can be incorporated to improve predictive accuracy. We will additionally explore how performance varies when using a composite outcome versus developing different models for individual outcomes (e.g., sepsis, pre-eclampsia). This may be informed by the results from WS2. Where appropriate, we will consider using a least angle selection and shrinkage operator (LASSO) penalty (67).

In parallel we will investigate and compare ML approaches to developing a prediction model, including methods such as random forests, deep neural networks, Bayesian Gaussian processes and gradient-boosted decision tree survival models (37,68). Such models allow consideration of interactions between available variables providing “latent variables” (complex, non-linear transformations of the original input variables) that may improve prediction performance over the non-transformed input variables. We will prioritise principled, probabilistic methods that permit the incorporation of prior clinical knowledge, such that results are “interpretable”, avoiding the “black box” nature of much ML-oriented research in this area (68,69).

MOEWS are typically calculated several times during a woman’s pregnancy, and other candidate variables will also be measured repeatedly (for example, blood tests). The best way of accounting for these repeated measures in model development (and validation) is not well defined. Therefore, we will explore different options for how best to incorporate this.

Where applicable learning from the regression and machine learning approaches will be combined to achieve a final deliverable model.

11.2.4.2 Missing data

Missing data will occur in all medical research with not all patients providing data on all predictors of interest. To avoid excluding patients and reducing the sample size, multiple imputation will be used to impute missing values, under a missing at random assumption.

Identifying the true underlying missing data mechanism from the available data is rarely possible. Assumptions need to be made on the plausible mechanism, and approaches needed to be used. Under a missing completely at random mechanism (MCAR), the missingness mechanism does not depend on unobserved (unseen) data. Carrying out a complete case analysis will produce unbiased estimates (but

with a loss of precision if full data are observed) but will reduce sample size. Under the missing at random (MAR) assumption, the missingness after conditioning on the observed data does not depend on the unobserved (unseen) data. Under this approach, we can apply approaches such as multiple imputation, by fitting a joint model to the observed data and impute the missing data, taking account of the uncertainty in the estimated parameters of this joint model. We feel this, MAR, approach makes a less strong and more realistic assumption than the MCAR approach. The MAR imputation model will include all variables considered for the multivariable model building, the outcome and any auxiliary variables that will help explain the missingness. When imputing missing values for predictors that are repeatedly measured (for example, vital signs) we will use methods that account for (and take advantage of) this structure in the imputation model. The assumption of a missing not at random (MNAR) approach whilst not implausible is considerably more complex to investigate – there is a dearth of research investigating MNAR in the context of prediction model research. We will nevertheless explore whether the MAR assumption holds by comparing the imputed values (after accounting for the observed values) and the missing values to identify if there are any systematic differences to suggest a MNAR assumption. We will explore patterns of missing data in key sub-groups (e.g., ethnicity) to detect any potential bias in data recording. We will also explore whether patterns of missingness (e.g. clinicians electing to perform specific blood tests) could be utilised to aid prediction (70).

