6 OBJECTIVES AND OUTCOME MEASURES

| Objectives | Outcome Measures | Timepoint(s) of evaluation of this outcome measure (if applicable) |
|---|--|--|
| Primary Objective To develop and validate an electronically embedded, data-enhanced Maternal Early Warning Score (eMOEWS) with clinical escalation pathways | Predictive performance of new early warning scores, assessed by: discrimination, calibration, and clinical utility. | During pregnancy or in the immediate postpartum period. |
| Secondary Objectives: | | |
| To define 'near-miss' and 'pre-near-miss' criteria for use with routinely-collected data to measure maternal outcomes. | 'Near-miss' and 'pre-near-miss' outcome criteria measurable using routinely available electronic data, assessed in NHS hospitals | During pregnancy or in the immediate postpartum period. |
| To assess performance of the new near-miss and pre-near-miss outcome criteria in 3 hospitals and MBRRACE-UK: 
 • a stratified random sample of 100 sets of records of near-miss and pre-near-miss cases across the three sites. • review hospital serious event systems for serious maternal events • Proportions of women meeting criteria | Descriptive statistics to describe whether the electronic criteria used correctly identified the conditions. Descriptive statistics of missed and captured events according to electronic criteria Descriptive comparison to published rates | During pregnancy or in the immediate postpartum period |
| To develop a large representative eight-twelve maternity unit cohort | Cohort developed and ready for assessment | 05/2029 |

| | | |
|--|--|---------|
| for model development and assessment | | |
| To investigate the performance of existing MOEWS/MEWS scores in the new maternity cohort and in women who have died or had severe morbidity in pregnancy | Evidence-based assessment of existing MOEWS, both in new retrospective (assessed by discrimination, risk of our key events at each MOEWS/MEWS level) and nationally recognised mortality/morbidity (assessed by sensitivity and duration of prior warning) cohorts | 05/2029 |
| To develop and validate an optimal vital-signs-only-based MOEWS | Relative performance of new MOEWS, best published MOEWS and NHSI national MOEWS for prediction of near-miss or pre-near-miss | 05/2029 |

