11.2.4.3 Assessment of model performance

The performance of both new models will be assessed through internal and external validation. The performance of a model in the development data is usually over-estimated. Internal validation techniques will be used to adjust for this ‘optimism’. The internal validity of the final models will also be assessed by the bootstrap re-sampling or k-fold cross validation techniques to adjust for over-optimism in the estimation of model performance. To ensure a meaningful comparison we will use the same internal validation procedures to compare statistical and machine learning models. The internal validation will quantify and be used to adjust the performance measures (e.g., discrimination, calibration) for any optimism. Heterogeneity in model performance will be explored across different hospitals using internal-external cross-validation (71).

We will use the performance metrics used in WS2 (i.e., discrimination, sensitivity, specificity, and the degree of advanced warning prior to an event). As discussed above, the performance of a prediction model is typically characterised by assessing both its calibration and discrimination. With our new models we will be able to assess model calibration as the new development models will provide risk estimates. Calibration reflects how close the predictions from the model are to the observed outcome frequencies, so represents a major step forward in assessing eMOEWS performance. It is a key performance metric recommended in TRIPOD (Transparent reporting of a multivariable prediction model for individual prognosis or diagnosis) guidance (72). Calibration will be assessed graphically, using a calibration plot, plotting observed outcomes against predictions using smoothing techniques. The plot will also be supplemented with results for individuals grouped by similar probabilities (tenths) comparing the mean predicted probability to the mean observed outcome. Calibration will also be quantified by calculating the calibration slope and intercept. The discrimination of the prediction models will be summarised with the concordance statistic (equivalent to the Area Under Receiver Operating Characteristic curve) with 95% confidence interval. Validation will include assessing for variation in performance between key sub-groups, as per WS2.

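### The planned check of the missing-at-random assumption (Protocol 11.2.4.2) compares imputed values with values nobody has; read as imputed versus observed, it still cannot support or refute MAR

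*Protocol*

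**What the plan says.** Protocol section 11.2.4.2 covers missing data for the new vital-signs score and the eMOEWS (Workstream 3b). The main approach is fixed: "multiple imputation will be used to impute missing values, under a missing at random assumption". Imputations are to come from a joint model fitted to the observed data. MAR is defined there in the usual way: once the observed data are conditioned on, missingness does not depend on the unseen values.

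The section concedes that "Identifying the true underlying missing data mechanism from the available data is rarely possible", and of the alternative it says "The assumption of a missing not at random (MNAR) approach whilst not implausible is considerably more complex to investigate". It then states that MAR will nevertheless be explored by "comparing the imputed values (after accounting for the observed values) and the missing values to identify if there are any systematic differences", and that such differences would point to MNAR.

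Two related activities are planned in the same section: describing missingness in sub-groups, and using it as information. On the second it says "We will also explore whether patterns of missingness (e.g. clinicians electing to perform specific blood tests) could be utilised to aid prediction".

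For the existing scores, section 11.2.2 (Workstream 2a) lists several treatments of missing vital signs, including setting them all to normal or all to abnormal. Section 11.2.3 carries these over to Workstream 2b. Section 11.2.4.2 does not state them for the new models.

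**The concern.** The stated comparator, the missing values, is by definition not in the data. If observed values were meant, the comparison answers a different question (does the imputation model fit?) from the one assigned to it (does MAR hold?). The inference from systematic differences to MNAR is therefore wrong on any reading, and it sits awkwardly with the section's own remark that the mechanism can rarely be identified.

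What is at stake is reassurance. The primary outcome measure in section 6 is "Predictive performance of new early warning scores, assessed by: discrimination, calibration, and clinical utility", and section 11.2.4.3 adds "Calibration will also be quantified by calculating the calibration slope and intercept". If the check reports no systematic differences, as it will under any mechanism when the imputation model fits, readers may take the calibration results to be protected against MNAR when nothing has been learned about that.

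**Working it through.** The plan gives no figure on this point, so there is none to reproduce. The argument is logical; the simulations only illustrate it.

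**Notation.** Let l be a predictor with gaps, o the observed data (other predictors and the outcome), and M = 1 if l is missing. MAR states that f(l | o, M=1) = f(l | o, M=0).

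**Step 1, as written.** The comparison needs l when M = 1. Those values are unobserved, so it cannot be computed.

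**Step 2, imputed versus observed, adjusted for o.** Imputed values l* are drawn from the model fitted to the observed cases, that is, from an estimate of f(l | o, M=0). Hence E[l* | o, M=1] - E[l | o, M=0] = 0 when that model fits. The left side of the MAR equation never enters. A non-zero result means the imputation model fits badly, not that data are MNAR.

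**Step 3, imputed versus observed, unadjusted.** The difference is the average of E[l | o, M=0] over o in the missing group minus its average over o in the observed group. It is non-zero when the groups differ on observed variables that predict l, which MAR allows.

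**Step 4, simulation.** The documents give no missingness rates or mechanisms, so all settings except the sample sizes and event rate are assumptions.
- From the Protocol (section 11.3): development n = 293,200, validation n = 164,300, event rate 2%.
- Assumed: one vital sign v and one laboratory value l, standard normal, correlation 0.3; logit risk = a + 0.75v + b·l with b = 0.40 or 0.75; 25, 50 or 75% of l missing.
- Missingness logit slope: -1 on v (MAR), or ±0.5 or ±1 on l (weak or strong MNAR, both directions).
- 2 × 3 × 5 = 30 settings, 6 replicates, 3 imputations; l imputed from v and the outcome with parameter draws.

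| Quantity (SD units of l) | MAR true | MNAR true |
|---|---|---|
| Adjusted imputed minus observed (what the check sees) | -0.002 to 0.002 | -0.002 to 0.002 |
| Adjusted true missing minus observed (known only in simulation) | -0.004 to 0.002 | 0.43 to 0.79 in size |
| Unadjusted imputed minus observed | -0.254 to -0.244 | 0.041 to 0.078 in size |

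The adjusted check misses the whole MNAR gap. The unadjusted check looks worse when MAR holds.

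**Step 5, a second design.** With n = 200,000, one covariate correlated 0.5 with the predictor, about 40% missing, logit slope 1 and one imputation, the adjusted difference was 0.001 (MCAR), 0.008 (MAR) and 0.003 (MNAR), SE 0.004 each. The true adjusted gap under MNAR was 0.65. The unadjusted difference was 0.00, 0.43 and 0.19. The conclusion is the same.

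**Step 6, what the check could leave hidden.** In the 30 settings the calibration intercept from MAR-imputed validation data was -0.025 to 0.010. Among women whose test was actually measured, with the MAR-developed model applied to real values, it was:
- -0.017 to 0.011 under MAR;
- 0.042 to 0.371 (observed/expected 1.04 to 1.41) when low values go untested;
- -0.075 to -0.502 (observed/expected 0.93 to 0.62) when high values go untested.

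Standard errors were 0.019 to 0.050. This measured-only calibration can also move if missingness depends on the outcome, so it is an illustration and not itself a test of MAR.

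**The case against.** **The check is exploratory.** This stands. Imputation under MAR goes ahead whatever it shows, the section already warns about identifiability, and the reference to missing values is probably a slip for observed values. But Steps 2 and 3 show that correcting the slip does not rescue the inference.

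**The calibration errors do not come from this sentence.** This also stands. A reader might infer from Step 6 that the sentence causes intercept errors of up to 0.371 or -0.502. It does not: they arise from imputing under MAR when data are MNAR, and rewording the sentence would leave them unchanged.

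**The SAP may contain an MNAR sensitivity analysis.** It may; section 11.1 leaves detail to it and it is not at hand. A reader might infer that the plan has no such analysis. The Protocol alone cannot support that, and it is not the point made here. The point is that the Protocol fixes an uninformative check and attaches a wrong inference to it.

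**Other planned work mitigates.** Partly. In a separate run at 50% missing and log-odds 0.75, adding missingness to the model brought the measured-women intercept from 0.145 (weak MNAR) and 0.224 (strong MNAR) to 0.011 and 0.006. That is one setting, and it does not show how far results depend on MAR. The auxiliary variables and repeated-measures structure planned in 11.2.4.2 may make MAR more plausible; the simulations have neither, so their calibration errors may not carry over.

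**Some missing values could be recovered.** Section 7.3.2.1 allows manual augmentation from paper records. Values absent electronically but found on paper could be set against imputations. The Protocol does not link the two, so this qualifies Step 1 without answering it.

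**Conclusion.** The point holds as a fault in the stated analysis, with a limited consequence. As written, the comparison cannot be made from the study data. Read as imputed versus observed, it is about zero after adjustment whatever the mechanism when the imputation model fits, and non-zero under true MAR when unadjusted. No version supports or refutes MAR.

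The logic does not depend on the simulation settings, although the size of the hidden gap does. The harm is possible false reassurance about calibration, a component of the primary outcome measure. It would go too far to say that the primary analysis is invalid or that MAR is wrong here; the documents give no missingness data from which to judge either.

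**What to change.** Replace the sentence in section 11.2.4.2 with wording such as: *MAR cannot be tested from the observed data; sensitivity of model performance to departures from it will be assessed by delta-adjusted (pattern-mixture) imputation of key predictors over a range fixed before analysis, in both directions.* Extending the normal/abnormal scenarios of section 11.2.2 to Workstream 3b is an acceptable alternative already present in the Protocol.

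- Report the change in calibration intercept, slope and c-statistic as a sensitivity range, not as an estimate of the mechanism. With the model fixed and validation imputations shifted from -1 to +1 SD (50% missing, log-odds 0.75), the intercept ran from 0.295 to -0.433 under MCAR and from 0.278 to -0.397 under strong MNAR. The ranges are nearly the same, so they show dependence on MAR without identifying the truth.
- Apply the shifts in development as well as validation where feasible; shifting validation data alone leaves the fitted model, and any error built into it, untouched.
- Keep any imputed-versus-observed comparison, labelled as a check of imputation-model fit.
- Keep the planned work on missingness by sub-group and as a predictor.

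Cost: one sentence of text and a small amount of extra analysis. Because repeated measures are imputed jointly, a shift in one variable should carry into others, so some re-imputation is needed. No new data are required, and section 11.1 has the SAP finalised before any analysis, so the range can be fixed there.

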11.2.4.3 Assessment of model performance

The performance of both new models will be assessed through internal and external validation. The performance of a model in the development data is usually over-estimated. Internal validation techniques will be used to adjust for this ‘optimism’. The internal validity of the final models will also be assessed by the bootstrap re-sampling or k-fold cross validation techniques to adjust for over-optimism in the estimation of model performance. To ensure a meaningful comparison we will use the same internal validation procedures to compare statistical and machine learning models. The internal validation will quantify and be used to adjust the performance measures (e.g., discrimination, calibration) for any optimism. Heterogeneity in model performance will be explored across different hospitals using internal-external cross-validation (71).

We will use the performance metrics used in WS2 (i.e., discrimination, sensitivity, specificity, and the degree of advanced warning prior to an event). As discussed above, the performance of a prediction model is typically characterised by assessing both its calibration and discrimination. With our new models we will be able to assess model calibration as the new development models will provide risk estimates. Calibration reflects how close the predictions from the model are to the observed outcome frequencies, so represents a major step forward in assessing eMOEWS performance. It is a key performance metric recommended in TRIPOD (Transparent reporting of a multivariable prediction model for individual prognosis or diagnosis) guidance (72). Calibration will be assessed graphically, using a calibration plot, plotting observed outcomes against predictions using smoothing techniques. The plot will also be supplemented with results for individuals grouped by similar probabilities (tenths) comparing the mean predicted probability to the mean observed outcome. Calibration will also be quantified by calculating the calibration slope and intercept. The discrimination of the prediction models will be summarised with the concordance statistic (equivalent to the Area Under Receiver Operating Characteristic curve) with 95% confidence interval. Validation will include assessing for variation in performance between key sub-groups, as per WS2.

We will explore risk thresholds to identify high risk (such that we predict poor outcome) and low risk (such that we predict good outcome) groups. We will compare performance of our models to those of published MOEWSs established in WS2a, including decision curve analysis. We will externally validate our models using new data from our collaborator sites collected in the two years following the derivation cohort. We will assess the model performance within key pre-defined sub-groups (including maternal age and ethnicity).

11.3 Sample Size Determination

11.3.1 Workstream 2a

We estimate the WHO “near-miss” event rate will be at least 10/1000 (2,3) and the severe morbidity event rate will be at least a further 10/1000 maternities (2,73) . Although rates of our less severe new ‘pre-near-miss’ will be higher we have calculated our sample size based on these severe event rates alone. The retrospective cohort will include four years and two months' worth of data from up to 12 sites. We anticipate that there will be 5875 births on average per site per year. Therefore, we will have approximately 293,200 births in the retrospective cohort, of whom 2932 will have a near-miss and at least a further 2932 will have pre-near-miss events. Guidance suggests that at least 100 events are required for model validation (74). Therefore, our sample size (which is driven both by the need for adequate representation in subgroups and the requirements of WS3, see below) should be more than sufficient to generate robust performance metric estimates, including in key subgroups and for the secondary outcomes (see model performance in key subgroups WS3b below – note that the retrospective cohort is larger than the prospective cohort and therefore the number of events per subgroup will be even higher).

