2 LAY SUMMARY

Every year more than 700,000 women give birth in the United Kingdom. Of these at least 8700 nearly die – called a “near-miss”, and 70 die. Many more women suffer harm, often with effects lasting for life. Women from less wealthy areas and particular ethnic groups are more likely to come to harm.

“Vital signs” include measurements of blood pressure, heart and breathing rates. Doctors and midwives use tools that score vital signs to spot women becoming unwell. These tools are called “Modified Obstetric Early Warning Scores” (MOEWS). Despite their use, poor outcomes still occur. This may be because MOEWS use only the most recent vital signs. Using extra data like blood tests may help spot unwell people earlier.

We aim to reduce poor outcomes for women giving birth. We will find better ways of describing, spotting, and treating women becoming unwell.

We plan four linked projects to develop an electronic advanced maternal obstetric early warning system (eMOEWS). Patient and Public (PPIE) collaborators have developed this work with us. We will work closely with them throughout this project.

Once we have completed these four projects, we plan to carry out a trial to assess whether the new eMOEWS leads to better outcomes than the existing tools. This trial will be described in a separate protocol.

Project One

We will develop new definitions of worsening illness in women giving birth. We will work with our PPIE colleagues and other experts, reviewing published work. This will help staff use routinely collected health data to spot early illness, before a woman becomes very unwell. We will check that the new definitions reliably identify women becoming unwell.

Project Two

Using the new definitions, we will test how well current MOEWS pick up worsening illness. We will use data from eight to twelve NHS maternity units serving diverse women, and our national maternal review programme.

Project Three

We will develop an advanced, electronic MOEWS (eMOEWS) working with our PPIE collaborators and other experts. This will use extra information known to affect the risk of poor outcomes. We will test how well the eMOEWS spots worsening illness, using our new definitions.

Project Four

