5 BACKGROUND AND RATIONALE

5.1 What is the problem being addressed?

Of over 700,000 women giving birth in the UK annually, one in every 10,000 women dies during or up to six weeks after pregnancy (1). For every woman that dies, 120 will have a 'near-miss' (8,700 women annually) often with lifelong sequelae (2). Recent data from the United States using adapted Centre for Disease Control definitions found even higher rates (2%) (3). There are significant disparities in maternal and perinatal outcomes between ethnic, age and socioeconomic groups (1,4). Maternal mortality has been consistently shown to be more than four-fold higher among women from Black ethnic groups, and two-fold higher among women from Asian ethnic groups compared to women from White ethnic groups (5). Mortality rates are similarly two-fold higher amongst women who live in the 20% most deprived areas compared to those who live in the least deprived areas (5). Women aged over 40 are four times more likely to die during or after pregnancy compared to women aged 25-29 (5). Substantial disparities also exist in severe maternal morbidity; a recent analysis by our group (manuscript submitted) using Hospital Episodes Statistics data has shown that severe maternal outcomes at the time of a childbirth event, measured using the English Maternal Morbidity Outcome Indicator (EMMOI) are up to 70% higher amongst women from Black Caribbean and Black African ethnic groups. This disparity persists across all English regions and is driven primarily by sepsis and complications related to haemorrhage or pre-eclampsia. This variability, along with the major underlying causes, suggest a high degree of avoidability, a suggestion strongly supported by MBRRACE-UK mortality reports (5).

Current published morbidity criteria (6-9) represent near end stage (near death), rather than early deterioration and are not reliably derivable from routine data, preventing both development of early warning systems to detect early maternal deterioration and effective routine quality assurance.

The detection of women at risk of severe maternal morbidity or mortality is currently limited by the use of expert opinion-based Modified Obstetric Early Warning Scores (MOEWS). These MOEWS are based only on the most recent set of vital signs (heart rate, blood pressure, oxygen saturation, respiratory rate,

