7.3.3.3 Outcome measures

The primary outcome for MOEWS assessment for both data sources (WP2a&b) will be a combination of maternal death, 'near-miss' and 'pre-near-miss' events (as defined in WS1). Secondary outcomes will be maternal death, 'near-miss' and 'pre-near-miss' events, individually. For more details on the analysis methods see Section 11.2.3.

7.4 Workstream 3

Workstream 3 will develop an eMOEWS candidate variable list by literature review informing a further Delphi process. An optimal vital-signs MOEWS and a multivariable eMOEWS will be developed and validated, exploring regression models and machine learning (ML) approaches.

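### Section 11.3.1 calls the retrospective cohort sufficient for all secondary outcomes, but for maternal death alone it expects only about 20 to 29 events against the 100 the section itself cites

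*Protocol*

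**What the plan says.** **Outcomes.** Protocol section 7.3.3.3 sets the outcomes for assessing existing MOEWS: "The primary outcome for MOEWS assessment for both data sources (WP2a&b) will be a combination of maternal death", together with near-miss and pre-near-miss events. It continues: "Secondary outcomes will be maternal death", near-miss and pre-near-miss, each taken individually. Death alone is therefore a secondary outcome.

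**Sample size.** Section 11.3.1 bases the retrospective cohort on up to 12 sites, 5875 births per site per year and four years and two months, giving about 293,200 births. It expects 2932 near-miss events and at least 2932 pre-near-miss events. It then sets a yardstick, "Guidance suggests that at least 100 events are required for model validation", and concludes that the sample "should be more than sufficient to generate robust performance metric estimates, including in key subgroups and for the secondary outcomes". No outcome is excepted, and the protocol gives no expected number of deaths.

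**Death rate.** Section 5.1 states that "one in every 10,000 women dies during or up to six weeks after pregnancy". The lay summary agrees: "Every year more than 700,000 women give birth in the United Kingdom", of whom 70 die.

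**Sites.** The lay summary gives a range: "We will use data from eight to twelve NHS maternity units serving diverse women".

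**The concern.** The 100-event yardstick is met many times over by near-miss and pre-near-miss events, and the conclusion is then extended to every secondary outcome. Death is about a hundred times rarer than the near-miss rate used in the calculation (1 against 100 per 10,000), so it cannot inherit that conclusion.

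Section 11.2.2 plans sensitivity, specificity and a c-statistic for each MOEWS. A reader of 11.3.1 would take the results for death to be as robust as the others. They would rest on a few dozen events at most, and an apparent ranking of scores on death could be trusted more than it deserves.

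**Working it through.** **1. Reproduce the plan's figures.**
- Births: 12 sites × 5875 × (4 + 2/12) years = 293,750, against about 293,200 stated (0.2% apart).
- Near-miss events: 293,200 × 10/1000 = 2932, as stated.

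The stated counts are sound.

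**2. Death rate.** Section 5.1: 1 per 10,000. Lay summary: 70 / 700,000 = 1 per 10,000. A third route, also from section 5.1, is 8,700 near-misses a year at 120 per death: 8,700 / 120 = 72.5 deaths per 700,000, or 1.04 per 10,000.

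**3. Expected deaths in the retrospective cohort** (births × rate).

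| Sites | Births | Expected deaths | 95% Poisson range | Shortfall against 100 |
|---|---|---|---|---|
| 12 | 293,200 | 29.3 | 19 to 40 | 100 / 29.3 = 3.4-fold |
| 8 | 8 × 5875 × 50/12 = 195,833 | 19.6 | 11 to 29 | 100 / 19.6 = 5.1-fold |

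The slightly higher rate from the third route gives about 30 and 20. With 29 deaths expected, the Poisson probability of seeing 100 or more is below 1 in 10^23. Expecting 100 would take 100 × 10,000 = 1,000,000 births, or a death rate in 293,200 births of 100 / 293,200 = 3.4 per 10,000, which is 3.4 times the protocol's figure.

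**4. Precision for a single score.** The protocol gives no performance figure for death, so the values here are assumptions. One score per woman is also assumed.

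*c-statistic.* Hanley-McNeil: SE² = [A(1−A) + (n₁−1)(Q₁−A²) + (n₂−1)(Q₂−A²)] / (n₁n₂), with Q₁ = A/(2−A), Q₂ = 2A²/(1+A), n₁ deaths and n₂ survivors. The half-width is 1.96 × SE.

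| Deaths | SE at A = 0.80 | Half-width at A = 0.80 | Half-width at A = 0.70 / 0.90 |
|---|---|---|---|
| 20 | 0.060 | 0.12 | 0.13 / 0.09 |
| 29 | 0.050 | 0.10 | 0.11 / 0.08 |
| 100 | 0.027 | 0.05 | 0.06 / 0.04 |

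*Sensitivity near 80%, exact (Clopper-Pearson) 95% interval.*
- 16/20: 56% to 94%
- 23/29: 60% to 92%
- 80/100: 71% to 87%

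**5. Subgroups.** The sentence also covers key subgroups. Applying the ethnic proportions in section 11.3.2 at a flat death rate gives 293,200 × 0.103 / 10,000 = 3 deaths among Asian women and 293,200 × 0.043 / 10,000 = 1.3 among Black women. Multiplying the latter by the relative risk of 4.9 quoted in that section gives about 6.

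**6. Where the claim holds.** Near-miss alone gives 2932 events at 12 sites and 2932 × 8/12 = 1,955 at 8. The composite, near-miss and pre-near-miss outcomes clear 100 overall by a wide margin.

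**The case against.** **The plan's arithmetic is right.** Every count stated in 11.3.1 reproduces. The fault is one overbroad clause, true for two of the three individual outcomes. That is a fair description, but the clause is still wrong for the third.

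**The reader is partly warned.** Section 11.3.1 says the size was calculated from the severe-event rates alone, lists only near-miss and pre-near-miss counts, and hedges its conclusion. The rarity of death is plain in section 5.1. Even so, the conclusion names the secondary outcomes without exception. Section 11.3.2 handles a similar case openly: it reports that the Mixed ethnic group, with 59 expected events, falls below 100.

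**The link to the retrospective cohort needs a short inference.** Section 7.3.3.3 sits under Workstream 2b, and the reference to both data sources is attached to the primary outcome. Reading the next sentence as covering both is the natural reading, and 11.3.1 itself speaks of secondary outcomes for Workstream 2a.

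**MBRRACE-UK supplies deaths.** It does, and section 11.2.3 plans to "calculate sensitivity at pre-defined thresholds and assess how early women alert prior to the events occurring". But section 7.3.3.1 expects nearly all those women to have had an event, so that cohort cannot give a specificity or a c-statistic, and it is not the cohort 11.3.1 describes.

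**The precision figures are for one score at a time.** This stands. MOEWS compared in the same women are paired, and the precision of a difference depends on the correlation between scores, which is not known. The intervals show how uncertain each estimate would be; they do not measure the uncertainty of a comparison. Repeated scores per woman would also change them.

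**100 events is guidance, and 11.3.1 is written for 12 sites.** Both are true. The 8-site figure is a lower bound, and the contradiction needs only 29 against 100. The protocol chose 100 as the basis for its claim.

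**Conclusion.** The concern holds. As written, section 11.3.1 credits the design with a property it lacks for one secondary outcome: about 29 maternal deaths are expected at 12 sites and about 20 at 8, against a cited minimum of 100. The conclusion rests on the protocol's national death rate applying at the study sites. Sites would need 3.4 times that rate to reach 100, and deaths not captured in the hospital records would lower the count. The precision figures further assume a c-statistic or sensitivity of about 0.80 for death; on that assumption an estimate would be about twice as imprecise as with 100 events.

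The reach is limited. The composite primary outcome, near-miss, pre-near-miss, the cohort size and model development are not affected. It is a correction that should be made because it governs how the results for death will be read.

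**What to change.** In section 11.3.1:

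1. Restrict the sufficiency statement to the composite, near-miss and pre-near-miss outcomes.
2. Add the expected number of maternal deaths: about 29 at 12 sites and about 20 at 8, below the 100-event guidance.
3. Say that performance for death alone in the retrospective cohort is descriptive, reported with confidence intervals, with an expected precision of roughly ±0.10 to ±0.12 on a c-statistic assumed to be 0.80, and read alongside the MBRRACE-UK sensitivity and lead-time results in section 11.2.3.

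The first two belong in the protocol because they correct what it states. The reporting detail in the third could sit in the SAP, provided 11.3.1 no longer implies that death meets the standard.

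The cost is one or two sentences, with no change to data, sample size or the primary analysis. The stated claim becomes less favourable. Enlarging the cohort is not a realistic alternative: 1,000,000 births at 12 × 5875 = 70,500 a year would take about 14 years.
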